7.1.1 Subgroup analysis for the primary endpoint

The consistency of the treatment effect will be evaluated by adding an interaction term between treatment effect, time, and omega-3 index to the model described above. The *p*-value for the comparison between the interaction model and the simpler model will be used to determine consistency.

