11 STATISTICAL METHODS

Descriptive statistics will be provided for all data broken down by medication (omega-3 fatty acids and placebo), group (patients who recovered from the depression, patients who did not recover) and visit. Mean, median, standard deviation, range and number of observations will describe continuous variables. Frequencies and percentages will describe discrete variables. All statistical tests will be carried out two-tailed; the alpha (level of significance) is 5%. Efficacy of the treatment will be assessed using a linear random coefficient regression model.

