5.1 Primary endpoints

- CDRS-R total score trajectories from baseline to week 36 (measured at baseline, 6, 12, 24, and 36 weeks)

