where time t is considered a factor (while also investigating possibility of linearizing time effect) and randomized treatment group (intervention) and the interaction between randomized treatment group and time are included as fixed effects. The baseline values of the minimization factors age, gender, and hsCRP, as well as baseline antidepressant use and omega-3 index are included as covariates. The baseline outcome measure is modeled in the response, not as a covariate. The terms b_{i0} , b_{i1} , and b_{s0} represent participant-specific random intercepts and slopes and site-specific random intercepts. The random effects are assumed to be normally distributed and an unstructured covariance matrix will be assumed. The error term $\varepsilon_i(t)$ is assumed to be normally distributed with mean zero and variance σ^2 , independent of the random effects and is independent over time. An overall treatment effect for CDRS-R score at 36 weeks ($\beta_1 + \beta_{11}$) will be reported with a 95% confidence interval and corresponding p -value.

The competing survival models for time to event r (intervention dropout or study dropout) take the form:

$$\lambda_{ir}(t) = \lambda_{0r} \exp\{\gamma_1 \text{intervention} + \alpha_r m_i(t)\}$$

where the cause-specific Cox models include intervention as a time-independent effect and the estimated true trajectory of CDRS-R as a time-varying effect. The parameters α_r measure the strength of association between the longitudinal outcome and risk of the corresponding dropout event.

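### SAP 7.1.1 judges consistency across the omega-3 index against a model with no index-by-time term, so a significant p-value can reflect a prognostic index and a non-significant one can stand as consistency

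*SAP*

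**What the plan says.** SAP 7.1 writes out the longitudinal part of the primary model. Treatment, visit and "the interaction between randomized treatment group and time are included as fixed effects". Among the adjustment variables, age, gender and hsCRP at baseline appear, and the list ends: "as well as baseline antidepressant use and omega-3 index are included as covariates". The index thus has one coefficient, β16, and appears in no interaction. On the baseline score, the same section states: "The baseline outcome measure is modeled in the response, not as a covariate". The score is "measured at baseline, 6, 12, 24, and 36 weeks" (SAP 5.1), so β16 imposes the same index effect at baseline and at all four later visits.

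SAP 7.1.1 then assesses whether the treatment effect is consistent by "adding an interaction term between treatment effect, time, and omega-3 index to the model described above". Its decision rule is a single p-value, from a test described as the "comparison between the interaction model and the simpler model will be used to determine consistency". The section writes out neither model, and gives no list of tested terms, degrees of freedom, threshold, interaction estimate or treatment effect by index value. The 5% two-sided level comes from the general rule in Protocol section 11. SAP section 7 says in general that results will usually be given as point estimates with 95% confidence intervals.

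**The concern.** The only simpler model the SAP defines is the one in 7.1. It cannot represent an index that is related to how fast patients improve, whichever arm they are in. The larger model can represent this, wholly or partly. The p-value between them may then measure prognosis rather than differential benefit, and a uniform treatment effect would be reported as inconsistent.

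The opposite error is also open. A single p-value decides, so a non-significant one would stand as consistency in a trial sized for the main effect.

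At stake is the reading of the only subgroup analysis of the primary endpoint in the SAP. Protocol WH3b (section 5.2) names the index as a moderator. Protocol sections 4.1 and 4.3 also ask whether fatty-acid markers relate to illness course, so an index-by-time relation is a possibility the trial itself raises.

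**Working it through.** **Planned sample size.** No figure is given for this test. SAP 6.1 gives 111 per arm for a main effect of SMD 0.4 at 80% power. An exact two-sample t calculation gives 100 per arm; 111 is close to 100/0.9 = 111.1, that is, after 10% loss. The trial was sized for the main effect.

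**Terms in each comparison.** Five visits give four contrasts with baseline. Relative to the 7.1 model:

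- full factor expansion adds index × time (4), treatment × index (1) and treatment × time × index (4): 9 df;
- three-way terms only: 4 df;
- with index × time already in the comparator, the treatment-by-index terms are 1 + 4 = 5 df.

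**Assumptions.** The documents give no CDRS-R SD, correlation or prognostic strength. For illustration: n = 220, 1:1, complete data, random-intercept SD 7, random-slope SD 0.2 per week, residual SD 8. The week-36 variance is 7² + (36 × 0.2)² + 8² = 49 + 51.84 + 64 = 164.84, so the SD is 12.84. The index effect starts at zero and grows linearly to 2 or 3 points per SD of index at week 36, equally in both arms. That is 2/12.84 = 0.16 and 3/12.84 = 0.23 of the week-36 SD.

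**Formula.** The non-centrality λ is the drop in generalised least squares residual, Σ rᵢ′V⁻¹rᵢ, from the simpler to the larger model when both are fitted to the true means. The rejection rate is P(χ²(df, λ) > 95th centile of χ²(df)).

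**Inconsistency declared although the treatment effect is uniform:**

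| Comparison | 2 points per SD | 3 points per SD |
|---|---|---|
| Full expansion against 7.1 model, 9 df | λ 5.8: 33% | λ 13.1: 71% |
| Three-way terms only, 0/1 coding, 4 df | λ 2.7: 22% | λ 6.1: 48% |
| Three-way terms only, −0.5/+0.5 coding, 4 df | λ 0: 5% | λ 0: 5% |
| Index × time in comparator, 5 df | λ 0: 5% | λ 0: 5% |

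If the index effect is constant from baseline, β16 absorbs it and even the 9-df comparison rejects in 5%.

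**Cross-check by simulation** of the linear mixed part (220 patients, 432 runs per scenario, total SD 1 at week 36, with intercept, slope and residual carrying 0.4, 0.3 and 0.3 of the variance). For a prognostic change of 0.1, 0.2 and 0.3 SD per SD of index, rejection was 18%, 63% and 97% with 9 df; 16%, 41% and 74% with three-way terms and 0/1 coding; and 24%, 64% and 92% with linearised time. With index × time in the comparator it was 5-6%.

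**Power of a correctly targeted test.** True heterogeneity growing to 2.5 points per SD at week 36 gives λ 2.7. Power is 20% on 5 df, or 37% on 1 df with linear time. In the simulation, an effect running from 0.6 to 0.2 SD between −1 and +1 SD of the index was detected in about 23% of runs.

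For the split in WH3b, take 111 per arm, 80% with an effect of 0.5 SD and 20% with none (average 0.8 × 0.5 = 0.4). SE = √(2/88.8 + 2/22.2) = 0.336; power = Φ(0.5/0.336 − 1.96) = 32%; 95% CI half-width = 1.96 × 0.336 = 0.66 SD, wider than the 0.4 SD effect used for sizing.

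**The case against.** SAP 7.1.1 is short, and its authors may have meant a simpler model that already holds all two-way index terms. The false-inconsistency half would then disappear. The text does not say so, and the only model it points back to lacks those terms.

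The size depends strongly on the reading. The 33-71% belongs to the full expansion, although 7.1.1 speaks of one added interaction term. Three-way terms alone give 22-48% with 0/1 coding and no inflation with centred coding. A reader might infer 0/1 coding from "An overall treatment effect for CDRS-R score at 36 weeks" being defined as β1 + β11, but any coding with a one-unit gap between arms gives that contrast. The SAP does not state its coding; 0/1 is a common default, nothing more. This limits the claim, and it also shows that the result of the test turns on something unspecified.

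The variances and the 2-3 points are assumptions. An index unrelated to change over time does no harm.

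Low interaction power is common to subgroup analyses and is not itself an error. What can be criticised is letting non-significance settle consistency. The general preference for confidence intervals helps, but 7.1.1 still rests the decision on the p-value.

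A reader might also infer that the index is the moderator the protocol expects to matter most. The documents do not rank it so: Protocol 3.1.6 and 3.7 stress inflammatory markers, and WH3c calls EPA metabolites a strong predictor.

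**Conclusion.** The concern holds for the comparison as written. Following 7.1.1 literally against the 7.1 model can produce a significant result with no treatment heterogeneity, provided the index predicts change over time and the tested terms are the full expansion or 0/1-coded three-way terms. The direction follows from the missing index-by-time terms; the rates (33-71% and 22-48%) rest on the assumed variances and prognostic strength. The survival submodels, site effects and dropout were not modelled.

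The documents do not support the stronger reading that the planned test is shown to be invalid: the tested terms and the coding are unstated, and some admissible choices hold the 5% level. Separately, with power of about 20% for 2.5 points per SD under the same assumptions, about 80% of such trials would be called consistent.

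The point deserves correction because the rule can lead to a wrong conclusion in either direction and the repair is cheap. It concerns a secondary analysis and leaves the primary conclusion untouched.

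**What to change.** Leave the primary model in SAP 7.1 as it is. In 7.1.1:

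- Write out both models and the treatment coding. State a separate comparator: the 7.1 model plus index × time.
- Test only the terms that carry treatment × index, namely treatment × index and treatment × time × index, and state the degrees of freedom and significance level.
- Report the interaction estimate and the week-36 treatment effect, each with a 95% CI, the latter at pre-specified index values. The 4 and 5 of WH3b are natural candidates, but must be reconciled with the 3, 5 and 8 in Protocol 11.4.1.
- State that a non-significant result will not be described as consistency; the reading should rest on the interval.

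The cost is a few sentences in the SAP, one extra model fit and four more nuisance parameters for index × time. No new data are needed. The change does not cure the low power; it lets the reader see how much heterogeneity the data leave open.

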7.1.2 Sensitivity analyses for the primary endpoint

1. **Typical ITT analysis:** In order to compare results with other trials, the linear mixed model part of the analysis model above will be applied to the full analysis set, with all participants analyzed as randomized. The data from intervention dropout participants will be used as observed, i.e, the outcomes observed while on non-randomized antidepressants will be used. The mixed model assumes that missing data is missing at random. This analysis is expected to be biased toward the placebo arm, as the number of participants requiring antidepressants is expected to be higher in the placebo arm and the additional antidepressant will improve outcomes.
2. **Modified ITT analysis:** The first sensitivity analysis will be repeated, but the data from intervention dropout participants will be considered missing in the mixed model upon non-randomized antidepressant initiation/dose increase. The responses of participants with missing data will be assumed similar to those with complete data and similar covariate characteristics. The bias resulting from imbalance in the use of non-randomized antidepressants across treatment groups is curtailed, but the amount of data available for analysis, and therefore power, is diminished.
3. **Typical PP analysis:** In order to address the efficacy estimand, the sensitivity analysis model above will be applied to all full analysis set data during which participants were 'on protocol'. This means the participants are adhering to the treatment they were randomized to and are not using additional antidepressants. Non-compliers and those taking non-randomized antidepressants are excluded completely (i.e., complete case analysis). This yields an estimate of efficacy that is unbiased under the MAR assumption. It assumes that participants with missing data (those with additional antidepressants and those not adhering to randomized treatment) would have had similar outcomes to participants completing the study in the same treatment arm and with similar baseline characteristics and score trajectories. However, the use of additional anti-depressants is not considered to be random across participants, but rather related to intermediate outcomes and possibly treatment assignment. Selection bias is then expected to affect this estimate. Additionally, the reduction in participants decreases the power to detect a treatment effect.
4. **Delta-based multiple imputation for MNAR analysis:** The data after intervention dropout or study dropout is considered to be missing. Multiple imputation under MAR will be performed separately within each treatment arm (White et al 2011) using imputation models containing the minimization factors, baseline antidepressant use and omega-3 index. It will be assumed that participants initiating/increasing non-randomized antidepressant use would have had worse outcomes than observed had they not used the non-randomized antidepressant. A range of mean differences δ from a 25% increase in CDRS-R score (25% worse outcome) to a 100% increase (by 25% increments) in the CDRS-R score in the intervention dropouts as compared to the observed cases will be considered. Delta will then be added to the imputed

CDRS-R scores for the participants with intervention dropout. Results will be combined using Rubin's rule. This is repeated for each delta.

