11.4.1 Datasets to be Analysed, Analysis Populations

The intention-to-treat (ITT) approach includes all randomized patients. In order to account for the effects of antidepressant medication we will perform following analyses: The anticipated proportion of patients receiving additional antidepressants at some point during follow-up is estimated to be around 30%. The analysis of treatment efficacy of Omega-3 fatty acids needs to address that patients received additional antidepressants, and we propose the following analyses:

- Perform analysis according to intention to treat (ITT) principle by including all randomized patients according to their treatment groups and accounting for additional antidepressant use by jointly modeling the time to this event.
- Sensitivity analyses will be performed in which (i) all data are used as collected and actual missing data is multiply imputed based on MAR assumptions, (ii) all patients are used, but data upon additional antidepressant use are also considered missing and multiply imputed, (iii) entire follow ups from drop outs and participants initiating additional

antidepressants are removed (complete case, per protocol), and (iv) all participants are included according to randomization and delta-based multiple imputation is used for data after additional antidepressant use.

- Perform primary endpoint analysis considering the outcomes of patients with additional antidepressant prescription as missing values (from the time point of the antidepressant prescription).
- Both analyses described above will be prone to bias, because there might be differential antidepressant prescription, related to treatment group. In the efficacy analysis of the outcomes additional antidepressant prescription should not be ignored. We propose an approach in which the “missing” outcomes of patients with antidepressant prescriptions will be multiply imputed. By this approach, we mimic observations of depression scores that one would have received without antidepressant prescription. We plan to perform 10-fold multiple imputation. The missingness generating mechanism is considered to be “missing not at random” (MNAR), so the imputation method will need to address this. A method proposed by S. Jolani and S. van Buuren, 2013) is the “drawn indicator method” for missingness not at random.
- Sensitivity analyses of the results will reveal the dependence of the results on specific assumptions during the multiple imputation process.

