4.2 Secondary estimand

Efficacy (i.e., 'du jure', 'hypothetical') estimand The efficacy estimand quantifies the average treatment effect of EPA-rich Omega-3 relative to placebo over 36 weeks, as an adjunct to the German S3 guideline standard of care, if all randomized subjects had adhered to the randomly assigned treatment for the entire trial duration.

5 Endpoints

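### SAP 7.1.2 item 3, the analysis labelled for the efficacy estimand, is worded two ways, and its MAR claim does not generally hold for the complete-case version

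*SAP*

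**What the plan says.** The secondary estimand (SAP 4.2) is the effect "if all randomized subjects had adhered to the randomly assigned treatment for the entire trial duration". It concerns everyone randomized. SAP 7.1.2 item 3, the per-protocol analysis, is introduced as the one that addresses it.

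Item 3 gives two data rules. The mixed model is first "applied to all full analysis set data during which participants were 'on protocol"', which keeps a participant's scores until the deviation. Two sentences later: "Non-compliers and those taking non-randomized antidepressants are excluded completely (i.e., complete case analysis"). Protocol 11.4.1, sensitivity analysis (iii), sides with the second rule: the whole follow-up of drop-outs and of participants starting additional "antidepressants are removed (complete case, per protocol").

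The SAP then states: "This yields an estimate of efficacy that is unbiased under the MAR assumption". It explains MAR as meaning that participants with missing data "would have had similar outcomes to participants completing the study in the same treatment arm and with similar baseline characteristics and score trajectories". It adds that antidepressant use is not random but "rather related to intermediate outcomes and possibly treatment assignment", and concludes: "Selection bias is then expected to affect this estimate".

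**The concern.** The two data rules define different analyses, and two statisticians following item 3 could report different numbers for the efficacy estimand.

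The MAR sentence follows the complete-case rule, for which it is generally wrong. A likelihood mixed model is valid under MAR because the scores that preceded the missingness stay in the likelihood. Item 3 itself conditions on score trajectories. If participants who start an antidepressant are deleted outright, their trajectories go too and nothing remains to condition on.

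The caveat does not repair this. Dependence on observed intermediate scores and on arm is itself a MAR mechanism. The SAP therefore ascribes the bias to antidepressant use not being random, when deletion produces bias even where MAR holds. A reader would conclude that the estimate is sound if MAR is accepted, and it need not be.

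**Working it through.** No stated figure is attached to this claim, so the check is of the statistical property.

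**Algebra.** Let R = 1 for a participant who never deviates. Within an arm, for the week-36 score Y:

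mean(Y | R = 1) − mean(Y) = Cov(Y, R) / P(R = 1).

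If higher scores lead to antidepressant start, the covariance is negative and the retained group looks too well. The treatment contrast is biased by the difference between the two arms' terms. Under MAR the covariance runs through earlier observed scores. A model that keeps those scores can correct for it; a complete-case model cannot.

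**Inputs from the documents.** Visits at 0, 6, 12, 24 and 36 weeks (SAP 5.1); about 30% starting antidepressants, with more use hypothesised in the control arm (SAP 1); 1:1 allocation (SAP 6); standardized difference 0.4 (SAP 6.1).

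**Assumptions not in the documents.** Random intercept and slope plus independent error; week-36 SD about 12.3; true effect −4.8 points (about 0.4 SD); log-odds of starting rising by 1 per 10 points of the last observed CDRS-R; excess placebo log-odds of starting of 0, 0.5 or 1.0. Starting depends only on observed score and arm, so MAR holds by construction. Non-compliance and the SAP's other covariates were not simulated. There were 1,000,000 participants per scenario.

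**Results, week-36 difference (omega-3 minus placebo), true effect −4.8.**

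| Excess placebo log-odds | Starting: placebo / omega-3 | Nothing removed | Complete case | Mixed model, data up to start |
|---|---|---|---|---|
| 0 | 31.4% / 28.6% | −4.76 | −4.52 | −4.76 |
| 0.5 | 36.6% / 23.4% | −4.84 | −3.79 | −4.85 |
| 1.0 | 41.2% / 18.8% | −4.80 | −2.98 | −4.80 |

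The complete-case bias against the same data with nothing removed is −4.52 + 4.76 = 0.24, −3.79 + 4.84 = 1.05 and −2.98 + 4.80 = 1.82 points, or 5%, 22% and 38% of the effect.

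**Where it comes from.** The placebo mean among complete cases is too low by 37.56 − 39.99 = −2.43, 37.19 − 40.02 = −2.83 and 36.76 − 40.00 = −3.24. The omega-3 shift is then −2.43 + 0.24 = −2.19, −2.83 + 1.05 = −1.78 and −3.24 + 1.82 = −1.42. Both arms are flattered, the placebo arm more.

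**True effect zero, same mechanism.** Complete case gives 0.00, +0.79 and +1.58; the mixed model on data up to the start gives about 0.

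**When complete case is sound.**
- Starting unrelated to scores: −4.79 to −4.84, no bias.
- Starting dependent on baseline score and arm (excess 0.5 and 1.0): −4.22 and −3.60 without baseline as a covariate, −4.84 and −4.79 with it. SAP 7.1 models baseline CDRS-R in the response, so once participants are deleted the complete-case model has no such adjustment.
- Starting dependent on the last observed score, baseline as covariate: −4.61, −4.32 and −3.96. Bias is reduced but remains.

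**Scale.** With 30% of 111 per arm removed, 77.7 remain, and the standard error is about 12.3 × √(2 / 77.7) = 1.97. The biases are about 0.12, 0.53 and 0.92 standard errors.

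**The case against.** The strongest reply is that the SAP misleads nobody: it names an assumption, doubts it, expects selection bias and warns of lost power. This stands in part. A reader might infer that the plan presents the estimate as free of bias in this trial, and the text does not support that. What remains wrong is the conditional claim and the cause given for the bias.

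Second, the hypothetical question does not rest on item 3 alone. The primary joint model (SAP 7.1) censors at antidepressant start or increase and at study exit for non-adherence. Items 2 and 4 also treat scores after antidepressant start as missing. None of these deletes participants. This stands: item 3 is the sole analysis for the efficacy estimand by label only. But that label decides which number is reported against the estimand.

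Third, the complete-case wording is explicit and Protocol 11.4.1 agrees, so the opening phrase of item 3 may be mere imprecision. That settles which rule was probably meant. It is also the rule for which the MAR sentence fails.

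Fourth, a reader might infer that the bias always pulls the estimate toward zero, or that complete-case analysis is always biased. Neither holds. Under a null effect with more placebo starters the estimate moves away from zero, against omega-3. Under a null with equal selection it cancels. There is none if exclusion is unrelated to outcome given the model covariates.

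**Conclusion.** The point holds as an error of wording and method in one of four sensitivity analyses. Item 3 is ambiguous between two analyses, and its MAR statement is generally false for the complete-case one. That version is unbiased only if exclusion is unrelated to outcome given the model covariates, a condition the SAP itself doubts.

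Size and direction cannot be fixed from the documents. Under the stated assumptions the bias was 0.24 to 1.82 points on a true −4.8. It ran against omega-3 when placebo starters predominated, which is the pattern the SAP anticipates. The larger values depend on the assumed arm difference in starting, for which the documents give no figure. The primary analysis is not affected.

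**What to change.** For the efficacy estimand, fit the mixed model to all full-analysis-set data up to the first deviation (antidepressant start or increase, or non-compliance) and treat later visits as missing. This is item 2 extended to censor at non-compliance. Attach the MAR statement to this analysis, conditional on arm, covariates and the scores observed before the deviation.

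Keep the protocol's complete-case per-protocol analysis as descriptive only. Delete its MAR claim, or limit it to exclusion unrelated to outcome given the model covariates.

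The model and data are unchanged, so the cost is SAP wording plus a recorded departure from Protocol 11.4.1 (iii). The downside is that the efficacy-estimand analysis becomes close to item 2. Censoring also needs one dated definition of non-compliance: the SAP (section 7, missing data) uses a share of pills taken and Protocol 8.4 uses missed days over two weeks, and these must be reconciled.
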